## E2 Schedule of Measurements

The baseline evaluation will encompass one, two or more visits in the time window 6 weeks prior to 2 weeks after CRT device implant/upgrade date. If the patient passes the eligibility screening and signs informed consent, their baseline evaluation will include echocardiogram, quality-of-life questionnaire, 6-minute hall walk, blood test, vital signs, ECGs, device interrogation and baseline demographic and medical history including chart review. After CRT device implant, participants will undergo physiologic evaluations at various (up to 10 or more) RV-LV offset settings including ECGs and echocardiography. The randomized CRT pacing assignment will be programmed.

The follow-up evaluation (usually 3-12 months) will encompass one or more visits and include echocardiography, quality-of-life questionnaire, 6-minute hall walk test, blood test, vital signs, ECGs, device interrogation, and follow-up medical history including chart review. The patients will continue to be in extended follow-up through review of their medical charts till the end of the study (12 months from date of CRT implant/upgrade of the the last study participant).

Table 2.  
**EPIC Study Calendar**

	Baseline Evaluation	CRT Evaluation	Follow-up Evaluation	Extended Follow-up
Timeline (w.r.t. date of CRT device implant/upgrade)	-6 to +2 weeks	0 to +2 weeks	3 to 12 months	Till study completion
Informed Consent	✓			
Medical History	✓		✓	✓
Vital Signs	✓		✓	

Echocardiogram	✓	✓	✓	
KCCQ-12	✓		✓	
6-Minute Hall Walk	✓		✓	
Blood Testing	✓		✓	
Device Interrogation	✓	✓	✓	
12-lead ECGs	✓	✓	✓	
Randomization		✓		
Adverse Event Monitoring	✓	✓	✓	✓

### **E3 Safety and Adverse Events**

#### **3.a Adverse Events and Reporting Requirements**

Any adverse or significant events including heart failure hospitalizations, incident arrhythmias, complications and deaths will be tracked during the study participation (i.e. from time of consent through completion of the study). A baseline evaluation of all subjects' current medical problems will be documented and evaluated using the reporting classifications below prior to any baseline procedures. Any exacerbation of these medical problems will be documented as an adverse event. All adverse events will be tracked from time of consent through completion of the study.

##### **i Adverse Event Definitions**

Term	Definition
Adverse Event (AE)	An unfavorable medical occurrence in a human subject including any abnormal sign, symptom, or disease.
Serious Adverse Event (SAE)	An adverse experience occurring that results in any of the following outcomes: 
 
a. Death
 
b. A life-threatening adverse experience
 
c. Inpatient hospitalization or prolongation of existing hospitalization
 
d. A persistent or significant disability/incapacity (i.e. a substantial disruption of a person's ability to conduct normal life functions)
 
e. A congenital anomaly/birth defect
 
f. Any other experience which, based upon appropriate medical judgment, may jeopardize the subject and may require medical or surgical intervention to prevent one of the outcomes listed above
 

Life-Threatening	An adverse experience that places the subject (in the view of the investigator) at immediate risk of death from the reaction as it occurred, i.e. it does not include a reaction that, had it occurred in a more severe form, might have caused death.
------------------	--

**ii Attribution, Anticipation, and Expectedness of AEs**

The terms for attribution, expectedness, and severity are defined as follows:

1) Attribution

Classification	Description
Definitely Related	The adverse event, incident, experience or outcome was definitely caused by the procedures involved in the research.
Probably Related	There is a reasonable probability that the adverse event, incident, experience or outcome may have been caused by the procedures involved in the research.
Possibly Related	There is a reasonable possibility that the adverse event, incident, experience or outcome may have been caused by the procedures involved in the research.
Unlikely Related	The adverse event, incident, experience or outcome was unlikely caused by the procedures involved in the research.
Unrelated	The adverse event, incident, experience or outcome was unrelated to the procedures involved in the research.

2) Anticipation

Classification	Description
Anticipated	Any incident, experience, or outcome that is anticipated to occur due to the research (i.e. procedures, investigational medication, etc.).
Unanticipated	Any incident, experience, or outcome that meets all of the following criteria: 
 
a. unexpected (in terms of nature, severity, or frequency) given (a) the research procedures that are described in the protocol-related documents, such as the IRB-approved research protocol and informed consent document; and (b) the characteristics of the subject population being studied;
 
b. related or possibly related to a subject's participation in the research; and
 

	c. suggests that the research places subjects or others at a greater risk of harm (including physical, psychological, economic, or social harm) related to the research than was previously known or recognized.
--	--

### 3) Expectedness

Classification	Description
Expected	Any adverse event that is a known or foreseeable risk associated with the procedures involved in the research or is an expected natural progression of any underlying disease, disorder, or condition.
Unexpected	Any adverse event occurring in one or more subjects in a research protocol, the nature, severity, or frequency of which is not consistent with either: 
 
a. the known or foreseeable risk of adverse events associated with the procedures involved in the research that are described in (a) the protocol–related documents, such as the IRB-approved research protocol, any applicable investigator brochure, and the current IRB-approved informed consent document, and (b) other relevant sources of information, such as product labeling and package inserts; or
 
b. the expected natural progression of any underlying disease, disorder, or condition of the subject(s) experiencing the adverse event and the subject’s predisposing risk factor profile for the adverse event.
 

### iii Noncompliance and Exceptions

Term	Definition
Noncompliance	Failure to follow an applicable regulation or institutional policies that govern human subjects research or failure to follow the determinations of the IRB. Noncompliance may occur due to lack of knowledge or due to deliberate choice to ignore regulations, institutional policies, or determinations of the IRB.
Serious Noncompliance	Noncompliance that materially increases risks, that results in substantial harm to subjects or others, or that materially comprises the rights or welfare of participants.
Protocol Exceptions	A planned deviation from the approved protocol that are under the research team’s control. Exceptions apply only to a single participant or a singular situation.

	Washington University central IRB pre-approval of all protocol exceptions must be obtained prior to the event for both the coordinating center and all participating sites. Participating sites must also follow their local IRB's guidelines for any submission that needs to be made to their local IRB.
--	--

All incidences of noncompliance and protocol exceptions will be tracked from time of IRB approval until the close of the study.

**iv Reporting Requirements**

The Washington University Human Research Protection Office (HRPO) requires that all events meeting the definition of unanticipated problem or serious noncompliance be reported as outlined.

The PI is required to promptly notify the IRB of the following events:

- Any unanticipated problems involving risks to participants or others which occur at WU or any BJH or SLCH institution that impacts participants or the conduct of the study.
- Noncompliance with federal regulations or the requirements or determinations of the IRB.
- Receipt of new information that may impact the willingness of participants to participate or continue participation in the research study

These events must be reported to the IRB within **10 working days** of the occurrence of the event or notification to the PI of the event. The death of a research participant that qualifies as a reportable event should be reported within **1 working day** of the occurrence of the event or notification to the PI of the event.

**3.b Safety and Compliance, and Medical Monitoring**

**i Investigator**

- In the unlikely event of any acute adverse events during device programming during study participation, they will be addressed in person by the investigator and plans communicated to the treating team. Any significant adverse events related to the research project will be reported to the data safety monitoring committee and the Washington University IRB. The above sections describes the plan for data and safety monitoring of the clinical trial and adverse event reporting to the IRB, to ensure the safety of subjects.
- No investigational treatments will be used for the study. Participants will receive a clinically indicated CRT device per routine care. The only treatment intervention is optimization of RV-LV offset (programmable setting of CRT system) guided by ECG within parameters on CRT devices and programming approved by the FDA.

**ii Independent Data and Safety Monitoring Committee**

An independent data and safety monitoring committee (DSMC) chaired by [name] will be appointed. [name] will choose 2 additional members including a statistician and an electrophysiologist. All members of the DSMC will be completely independent and not involved in the conduct of the study. The committee will have access to the study data, in order to determine patient safety.

[name]: [name] is an experienced advanced heart failure expert and Professor of Medicine at Washington University. In his clinical practice he follows many advanced heart failure patients and patients with CRT devices. He will be able to

---

adjudicate if heart failure outcomes are attributable to participation in the research study. He has experience in leading DSMC for other cardiovascular research studies.

Electrophysiologist: The electrophysiologist will be experienced in implantation and management of CRT devices. They will be able to adjudicate if any CRT related outcomes or other complications are attributable to participation in the research study.

Statistician: The statistician will be knowledgeable in interim safety analyses.

## **E4 Study Outcome Measurements and Ascertainment**

The primary outcome of LV end-systolic volume will be evaluated by blinded study personnel with echocardiography. For secondary outcomes, the patients will fill out quality-of-life KCCQ-12 questionnaire, undergo 6-minute hall walk test, and have blood draw for serum NT-proBNP.

## **F Statistical Plan**

### **F1 Sample Size Determination and Power**

We plan to randomize 200 patients that may require enrollment of up to **250 patients**. This gives us 80% power to detect a between-treatment difference of  $\geq 2 \pm 5\%$  in the % reduction in LV end-systolic volume from baseline with a 2-sided  $\alpha$ -error 0.05. Previous studies have shown that a reduction in LV end-systolic volume from baseline is associated with an improvement in clinical outcomes. As both the study and control arms will receive CRT, albeit with different approach to programming RV-LV offset, any statistical difference in reverse cardiac remodeling between the two RV-LV offset programming strategies will be clinically important.

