# **D Study Design**

## **D1 Overview or Design Summary**

Once the eligibility for the study is determined and patient has consented for participation, all study participants will undergo a baseline evaluation (within 6 weeks prior to 2 weeks after CRT device implant/upgrade). Echocardiogram, quality-of-life questionnaire, 6-minute hall walk, blood test, vital signs, ECGs, device interrogation and baseline demographic and medical history including chart review will be obtained. After CRT device implant/upgrade, participants will

---

undergo physiologic evaluations at various (up to 10 or more) RV-LV offset settings including ECGs and echocardiography. A randomized assignment using a random allocation table in REDCap will be used to program patients to (A) intervention or (B) control RV-LV offset setting. Patients will return for study follow-up between 3-12 months. Follow-up evaluations will include echocardiography, quality-of-life questionnaire, 6-minute hall walk test, blood test, vital signs, ECGs, device interrogation, and follow-up medical history including chart review. The patients will continue to be in extended follow-up through review of their medical charts till the end of the study (12 months from date of CRT implant/upgrade of the the last study participant).

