**Treatment and control arms:** All study patients will receive standard of care clinically indicated medical and device therapy per their treating physicians. After implant of a clinically indicated CRT device or upgrade of a preexisting pacemaker or defibrillator device to CRT system, participants will be randomized 1:1 to treatment arms (A) active intervention of programming individualized RV-LV pacing offset to optimize ECG or to (B) active control of nominally programming CRT device without RV-LV offset. Of note, both intervention and control treatment are active FDA-approved CRT therapies and no investigational device or programming will be used, and no clinically indicated treatment will be withheld from any patient. At any time, if in the judgment of the patient's treating physicians or the research team, any treatment including CRT programming different from the study protocol is necessitated for clinical reasons, the appropriate clinically indicated changes will be made. At the end of the study, if the participant is clinically doing well and the programmed CRT settings are deemed clinically appropriate they will be retained, else the CRT programming may be changed as per standard of care.

Enrolled participants who have a failed or unsatisfactory LV lead implant will not be randomized.

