### **2.b Exclusion Criteria**

1. Unable to comply with the study follow-up.
2. Life expectancy  $\leq 1$  year.

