## **2.g Early Withdrawal of Subjects**

- The participants may withdraw by telling the study team they are no longer interested in participating in the study or by sending in a withdrawal letter.
- The investigator might end a subject's participation in this research study earlier than planned. This may happen for no reason, because in the treating physician or study team's judgment it would not be beneficial for the participant to continue, because the participant's condition has become worse, or because the research has ended.

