## 2.i Data Collection and Follow-up for Withdrawn Subjects

All data collection and follow-up for the purposes of the study will be terminated for subjects withdrawn from the study. At the time of withdrawal, if the participant is clinically doing well and the programmed CRT settings are deemed clinically appropriate they will be retained, else the CRT programming may be changed as per standard of care.

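### The 80% power in F1 is attached to 200 randomised patients but needs about 199 with an evaluable follow-up echo, so loss after randomisation has almost no allowance

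*Combined protocol and SAP*

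**What the plan says.** F1 gives the target as "We plan to randomize 200 patients that may require enrollment of up to" 250. The next sentence takes the power from that target: "This gives us 80% power to detect a between-treatment difference of" at least 2 ± 5% in the percentage reduction of LVESV from baseline, at two-sided alpha 0.05. F2 compares percentage change from baseline between arms by t-test, so a patient counts only with both a baseline and a follow-up LVESV.

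D1 gives a reason for enrolling more patients than are randomised: "Enrolled participants who have a failed or unsatisfactory LV lead implant will not be randomized". On the primary echo it says: "Patients will return for study follow-up between 3-12 months". The study calendar (Table 2 in E2) puts randomisation at 0 to +2 weeks from implant.

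Under 2.g participants may withdraw, or the investigator may end participation, for instance because "it would not be beneficial for the participant to continue". Section 2.i then says: "All data collection and follow-up for the purposes of the study will be terminated for subjects withdrawn from the study". It goes on to the device: "At the time of withdrawal, if the participant is clinically doing well and the programmed CRT settings are deemed clinically appropriate", the settings are kept, and otherwise they may be changed. Neither F1 nor F2 gives a loss rate, an inflation factor or a method for missing follow-up.

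**The concern.** F1 attaches the power to patients randomised, but the t-test has the power of the patients analysed. The two agree only if nearly every randomised patient returns for an evaluable echo. Up to a year can pass between randomisation and that echo in a heart failure population. The protocol lets patients leave in that interval and stops collecting data when they do, and E3 tracks deaths.

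The 250 might be taken for the attrition allowance. As F1 words it, though, it is the enrolment that may be needed to reach 200 randomised, so it does nothing for losses after randomisation.

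What is at stake is how the trial is read. The IRB, the DSMC and later readers would take 80% as the power of the trial as run, and a neutral result would be judged against a figure that the design reaches only with almost complete follow-up.

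**Working it through.** **Inputs**
- Difference δ = 2 percentage points (F1).
- SD σ = 5 percentage points. F1 writes 2 ± 5% without labelling the 5%; it is read here as the between-patient SD in each arm.
- Two-sided alpha 0.05 (F1, F2); two-sample t-test on percentage change (F2); 1:1 allocation (2.e).
- 200 randomised, up to 250 enrolled (F1).
- Loss after randomisation: not given, so 5, 10 and 20% are assumptions.

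**Formula**

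For n₁ and n₂ evaluable patients, the noncentrality is λ = δ / [σ √(1/n₁ + 1/n₂)] with n₁ + n₂ − 2 degrees of freedom. Power is the probability that a noncentral t variable with that λ falls outside ± the 97.5% point of the central t.

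**Step 1: reproduce F1**

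At 100 per arm, λ = 2 / (5 × √0.02) = 2.828 and the critical value is 1.972, so power is 80.4%. The normal approximation gives 80.7%. F1's 80% is reproduced with all 200 analysed. A one-sided test would give 88.2%, so the two-sided reading fits.

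**Step 2: how many evaluable patients does 80% need?**

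Solving the same function for 80% gives 99.08 per arm, or 198.2 in total.

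| Evaluable (arms) | Power |
|---|---|
| 200 (100/100) | 80.37% |
| 199 (100/99) | 80.17% |
| 198 (99/99) | 79.97% |
| 197 (99/98) | 79.77% |
| 196 (98/98) | 79.56% |
| 195 (98/97) | 79.36% |

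The margin is one patient taken strictly, two if 79.97% is accepted as 80%, and four (196 evaluable) if 80% means rounded to a whole percent. By the normal approximation the requirement is 98.1 per arm, 197 to 198 in total, which leaves two or three.

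**Step 3: is the 250 the allowance?**

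With 250 evaluable patients power would be 88.3%, which is not F1's figure. The stated 80% goes with 200.

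**Step 4: power of 200 randomised under assumed loss**

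| Assumed loss | Evaluable | Power | Difference detectable with 80% power |
|---|---|---|---|
| 0% | 200 | 80.4% | 1.99 points |
| 5% | 190 | 78.3% | 2.04 points |
| 10% | 180 | 76.1% | 2.10 points |
| 20% | 160 | 71.0% | 2.23 points |

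If the 10% loss is uneven, power is 75.95% with 95 and 85 evaluable and 75.56% with 100 and 80, so imbalance adds little. Simulation with 50,000 trials per setting gave 80.6, 78.4, 75.9 and 71.0% for the four rows.

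**The case against.** The strongest reply is that F1 contains no error. Its figure reproduces, what is missing is an unstated assumption of near-complete follow-up, and the size of any shortfall depends on loss rates that the documents do not give. At 5% loss the cost is about 2 points of power, and every detectable difference in the table still rounds to 2. The line between 198 and 199 is finer than F1's whole numbers support. All of that is true. It bears on how serious the point is, and is why the shortfall is called modest. It does not supply an allowance, and even 5% loss (10 patients) exceeds the margin on every reading in Step 2.

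The unlabelled 5% matters at least as much. With 200 evaluable, an SD of 5.5 gives 72.5% power; with 10% loss, an SD of 4.5 gives 84.3%. So whether the trial ends below 80% depends on the SD as well as on loss. This stands as a condition on the figures. At any fixed SD, though, loss still lowers power: at SD 4.5 the same formula gives 87.8% without loss.

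The mitigation is real. The exclusions in 2.b remove patients with short life expectancy and those "Unable to comply with the study follow-up", and a window of 3 to 12 months, with more than one visit possible, means a missed date need not be a missing echo. These limit loss but do not make it zero.

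Finally, the sentence in 2.i on device settings could also describe a patient who leaves after implant but before randomisation. That is fair, so the sentence is supporting evidence only. The point does not need it, because 2.g and 2.h allow withdrawal at any time.

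**Conclusion.** The concern holds. F1's 80% describes about 200 patients with evaluable baseline and follow-up LVESV, but it is attached to 200 randomised, and no section allows for loss between randomisation and the follow-up echo. The arithmetic behind the 80% is correct; the gap is the missing allowance.

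The size is modest: roughly 2, 4 and 9 points of power at 5, 10 and 20% loss. These figures assume that 5% is the SD, that patients without a follow-up echo drop out of the t-test, and that loss is unrelated to outcome, so that the difference and SD stay as planned. The loss rates are illustrative. The point should be fixed because the stated power is relied on and the correction is cheap.

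**What to change.** Restate the power in F1, leaving enrolment, test and alpha as they are:

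1. Say that the 80% refers to about 200 patients with evaluable baseline and follow-up LVESV.
2. Add the figure for 200 randomised at a stated assumed loss. For example: *With 10% loss after randomisation (180 evaluable patients), power is 76% for a 2-point difference at SD 5, and the difference detectable with 80% power is 2.1 points.* The team should put in the loss it expects.
3. Write SD beside the 5%. This is an editorial clarification.

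The cost is one or two sentences and a slightly less favourable stated power (76% instead of 80% at an assumed 10% loss). No extra patients are needed.

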## **2.e Randomization Method and Blinding**

A 1:1 randomization scheme using a random allocation table in REDCap will be used. The patient and personnel assessing study outcomes will be blinded to the randomized assignment.

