### **F2 Statistical Methods**

The primary outcome of interest is the LV end-systolic volume. Secondary outcomes include quality-of-life (KCCQ-12), functional performance (6-minute hall walk distance) and a prognostic biomarker (serum NT-proBNP). We will perform **t-tests** to assess for differences in the % change from baseline in primary and secondary endpoints between treatment groups. Sub-analyses will evaluate for effect modification by subgroups based on ischemic vs. non-ischemic cardiomyopathy, sex, and magnitude of RV-LV offset based on ECG. We prespecify evaluation of the subgroup with ECG optimized RV-LV offset  $\geq 40$  msec. A two-tailed p-value 0.05 will be considered as threshold for statistical significance.

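### Section F1 equates statistical significance with clinical importance, and its reasons do not show that a small between-arm difference on a surrogate matters

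*Combined protocol and SAP*

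**What the plan says.** F1 plans 200 randomised patients and gives the design target: "This gives us 80% power to detect a between-treatment difference of" 2 ± 5% or more, on the scale of percentage "reduction in LV end-systolic volume from baseline", at two-sided alpha 0.05. It then offers two supporting statements: reduction from baseline has been associated with better clinical outcomes, and both arms receive CRT with different programming. From these it concludes that "any statistical difference in reverse cardiac remodeling between the two RV-LV offset programming strategies will be clinically important".

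F2 specifies t-tests "to assess for differences in the % change from baseline in primary and secondary endpoints between treatment groups" and adds: "A two-tailed p-value 0.05 will be considered as threshold for statistical significance". F2 does not mention clinical importance, a confidence interval or a minimum important difference, and no other section does so. C1 places LV end-systolic volume among surrogate endpoints, and C2 defends it as a surrogate for clinical outcomes.

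**The concern.** Read with F2, the sentence in F1 makes significance sufficient for clinical importance, whatever the size of the effect. Neither supporting reason carries that weight.

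- The association with outcomes concerns change from baseline in patients given CRT. The documents do not tie any particular between-arm difference, such as one or two percentage points, to patient benefit.
- An active comparator explains why a small difference is to be expected. It does not explain why any difference, however small, matters.

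Because the endpoint is a surrogate, importance to patients needs an argument about size. At stake is the wording of the conclusion. As written, the plan would support a claim of clinically important benefit from an interval that almost touches zero. It also gives no help with a non-significant result whose interval still contains a worthwhile effect.

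**Working it through.** **Inputs**
- 200 randomised (F1), allocated 1:1 (section 2.e), so 100 per arm.
- Difference of 2 percentage points and SD of 5 (F1). The text does not label ± 5%; reading it as the SD is an interpretation, tested in step 1.
- Two-sided alpha 0.05 and a two-sample t-test on percentage change (F1, F2).
- No loss after randomisation (assumption; the plan states no figure). D1 says that "Enrolled participants who have a failed or unsatisfactory LV lead implant will not be randomized", so the allowance of up to 250 enrolled appears to cover exclusions before randomisation, not later loss.

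**1. Reproduce the plan's power.** Standard error of the difference = 5 × √(2/100) = 0.707. Noncentrality = 2 / 0.707 = 2.83 on 198 degrees of freedom. Power is 80.4% by the noncentral t and 80.7% by the normal approximation, against the stated 80%. The normal formula requires 99 per arm, 198 in total, against 200. The agreement supports reading ± 5% as the SD.

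**2. Smallest significant observed difference.** t(0.975, 198) × SE = 1.972 × 0.707 = 1.394 points.

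**3. An observed difference of 1.4.** t = 1.4 / 0.707 = 1.98, p = 0.049. The 95% CI is 1.4 ± 1.394, that is 0.01 to 2.79.

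**4. How often this could arise (SD 5, 100 per arm)**

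| True difference | P(significant) | P(significant and estimate below 2) |
|---|---|---|
| 1.0 | 29% | 21% |
| 2.0 | 80% | 30% |

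The middle column is ordinary power. The last column shows that a significant estimate below 2 points is not an edge case.

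**5. Sensitivity of the smallest significant difference**
- Fewer analysed, SD 5: 1.43 with 190 in total, 1.47 with 180, 1.56 with 160.
- Larger SD, 200 analysed (assumptions): 1.95 at SD 7, 2.79 at SD 10, 4.18 at SD 15.
- It equals 2 when SD = 2 / (1.972 × √(2/100)) = 2 / 0.279 = 7.2.

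**6. What a 2-point claim threshold would do.** Suppose importance required both significance and an estimate of at least 2. If the true difference is exactly 2, the estimate falls on either side of 2 equally often. The claim would then succeed in about 80% − 30% = 50% of trials, against 80% for significance alone.

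**The case against.** The case for leaving the text alone has four parts.

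- **It is a rationale, not an analysis rule.** The sentence closes a sample-size section. F2 attaches only statistical significance to p 0.05, and the publication plan (section J) says nothing about interpretation. This stands in part: that the trial would actually report 1.4 points as clinically important is an inference. But F1 is the only place where the plan says what makes a difference important, and it says so without limit.
- **There is no contradiction with the 2-point target.** A reader might infer that F1 conflicts with itself, because a difference 30% below its own target would count as important. The documents do not support that. F1 gives 2 points as the difference it has 80% power to detect and nowhere calls it the smallest important one. With 80% power and two-sided 0.05, the smallest significant difference is always about 1.96 / (1.96 + 0.84) = 70% of the design difference. This objection stands in full.
- **The 1.4-point figure depends on the SD.** This also stands. Above an SD of about 7.2, no significant estimate can be below 2 points. The lack of a size criterion remains at any SD.
- **Small gains may be worth having.** Both arms are programmable settings of an already indicated device, section 2.f describes very little added risk from device evaluation, and KCCQ-12 and walk distance add clinical context. That is an arguable judgement, but it has to be made on the size and precision of the effect. It cannot be settled in advance for every significant result.

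**Conclusion.** The point holds as a defect of interpretation. F1 equates significance with clinical importance, and its reasons do not support this for a small between-arm difference on a surrogate. On the plan's inputs, the assertion would cover an observed difference of about 1.4 points with a 95% CI of about 0.0 to 2.8. That example assumes SD 5, 100 per arm and no losses. Losses down to 160 analysed move the threshold only to 1.56, whereas an SD of 10 moves it to 2.8.

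Two stronger readings are not supported. The plan does not breach its own minimum important difference, because it states none. Nor do the documents commit the sponsor to a particular form of words in the report. The test, the error rate and the stated power are unaffected. The change is worth making because it is cheap and alters what the trial may conclude.

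**What to change.** Delete the closing assertion in F1. In F2, add wording such as: *The between-arm difference in percentage change in LV end-systolic volume will be reported with its 95% confidence interval alongside the t-test. Clinical importance will be judged from the estimate and the interval, not from p < 0.05 alone.* The interval also shows whether a non-significant result leaves room for a worthwhile effect.

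Do not make 2 points the default importance threshold. The documents justify it only as a detectable difference, and step 6 shows the cost: the chance of a claim falls from about 80% to 50% when the true difference is 2. If the sponsor wants a numerical threshold, it should justify one and state its effect on power.

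The change is confined to wording in F1 and F2, with no effect on sample size, visits or data collection. The downside is that a small significant difference could no longer be called clinically important on significance alone.
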